Secondary outcomes will include neonatal death, postpartum haemorrhage and sepsis, in addition to the pharmacokinetics of sodium bicarbonate infusion in pregnant women. Details of measurements are in table 1.

The independent variables will include the sociodemographic, clinical, and obstetric characteristics of the study participants at different time points as indicated in table 1.

Table 1: Measurements to be taken from the participant samples

Activity/ procedure	Time in minutes							Comment
	Baseline (0)	30	60	90	120	150	At birth	
Metabolites (lactate & glucose)	X	X	X	X	X	X		Bedside using the RAPID Point 500e or YSTE-BG100 Blood gas analyzer
Blood gases (pH, pCO ₂ , pO ₂)	X	X	X	X	X	X	X	
Serum Electrolytes (Na ⁺ , K ⁺ , Ca ²⁺ , Cl ⁻)	X	X	X	X	X	X	X	
Umbilical cord blood for lactate							X	Bedside using the RAPID Point 500e or YSTE-BG100 Blood gas analyzer
Myometrial Lactate only collected at Caesarean section							X	Bedside using the RAPID Point 500e or YSTE-BG100 Blood gas analyzer
Creatinine	X							Total of 5 mL of venous blood will be taken to a central laboratory; these are part of the standard care for each patient.
Liver function tests (ALT&AST)	X							
Full blood count	X							
Amniotic fluid lactate*	X							Lactate Pro device
Bicarbonate concentrations in plasma	X	X	X	X	X	X	X	Bedside using the RAPID Point 500e or YSTE-BG100 Blood gas analyzer

[figure not shown]

Figure 2: Flow of participants in the trial from screening to analysis

Recruitment and data collection from participants

Participants: Obstructed labour will be diagnosed by either an obstetrician or medical officer using a definition of the American Association of Obstetricians and Gynaecologists (ACOG). In the first stage of labour, the participant should have cervical dilatation >6 cm with ruptured membranes, adequate contractions lasting >4 hours with no change in cervical dilatation or delay in the second active stage of labour (nullipara >2 hours, multipara >1 hour) with adequate uterine contractions. In addition, any two of: the obvious signs of severe obstruction such as caput formation, severe moulding, Bandl's ring, subconjunctival haemorrhages or an oedematous vulva.

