Randomisation: A sequence of random numbers will be generated by an independent biostatistician using an online randomization service at www.sealedenvelope.com in permuted block sizes of four, six and eight. An independent, off-site pharmacist will prepare and consecutively number identical study packages using

the generated random numbers. This will ensure that the allocation is concealed. At the study site, after gaining consent, the research midwife will take the next sequentially labeled study drug package and administer its contents to the eligible participant. Therefore, both the participants and data collectors will remain blinded throughout the study.

Intervention/ Comparator: Eligible participants will be randomly assigned to receive 100 mls (8.4g), 150 mls (12.6g) and 200 mls (16.8g) of 8.4% sodium bicarbonate solution, or placebo (50 mls of NS 0.9%) in a ratio of 1:1:1:1. The study drug (Sodium Bicarbonate 8.4% and Normal Saline 0.9%) will be contained in identical 25 mL glass vials (Neon Laboratories Ltd, Mumbai, India), administered intravenously as a single bolus dose. Since the average waiting time for CS in our labour ward is approximately 110 minutes [11], there will be no need for a repeat dose.

In addition, all patients will receive the available Ministry of Health recommended standard preoperative care for all patients with OL which includes antibiotic prophylaxis, intravenous fluid replacement (1.5 L of normal saline), bladder drainage and lying in left-lateral position as they are being prepared for caesarean section [23]. Details in flow diagram 1.

Data collection

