Dissemination and Publications															*	*	*	*

Pharmacokinetics of sodium bicarbonate

Study design: This will be a population-based pharmacokinetics study of sodium bicarbonate using plasma levels in pregnant women with obstructed labour. We propose to investigate the association between the exposure of various doses of sodium bicarbonate (i.e. 8.4g, 12.6g and 16.8g) in pregnant women with obstructed labour, and identify determinants to inform dosing policy guidelines.

Study population: We will establish a cohort of pregnant women with obstructed labour in Mbale regional referral hospital. Only mothers that consent to participate in the study will be included.

Data collection: Following the administration of sodium bicarbonate, a blood sample will be collected from the mother at time 30, 60, 90, 120 and 150 minutes and at the time of childbirth; and then umbilical cord blood will be collected at birth for testing. Consequently, the concentrations of sodium bicarbonate will be determined using liquid chromatography (HPLC) method with electrochemical detection as described by Rodriguez [19]. The HPLC analysis will be conducted at Busitema University Ministry of Science, Technology and Innovation supported laboratory. Data from the respective participants will include PK, socio-demographics, adverse events and other clinical parameters including weight and age.

Data analysis: Non-compartmental analysis will be used to analyse the intensive PK data for sodium bicarbonate and a population pharmacokinetic model will be developed to analyse the sparse PK data. Any disparate treatment approached, additional medications or relevant clinical information, will be captured and adjusted for in the model. We will use nonlinear mixed-effects modelling (also known as population PK) to interpret the sodium bicarbonate pharmacokinetic data and assess the effect of variation. PopPK modelling offers a semi-mechanistic platform to interpret PK data, in that it evaluates the effect of patient covariates on physiological PK parameters (such as clearance and bioavailability), as opposed to hydroxyurea concentrations summary values (such as AUC and C_{max}). The concentration-time data for the drugs of interest will be analysed using popPK (nonlinear mixed-effects) modelling in NONMEM.

References

1. Wray S: **Insights into the uterus**. *Experimental Physiology* 2007, **92**(4):621-631.

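### The pharmacokinetic plan assigns non-compartmental analysis to an undefined intensive dataset and states no handling of endogenous bicarbonate, although time-0 and placebo values are already scheduled

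*Combined protocol and SAP*

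**What the plan says.** The section on pharmacokinetics of sodium bicarbonate gives one schedule for every woman: "a blood sample will be collected from the mother at time 30, 60, 90, 120 and 150 minutes and at the time of childbirth", with cord blood at birth. Its data-analysis paragraph then splits the work in two. One part reads "Non-compartmental analysis will be used to analyse the intensive PK data for sodium bicarbonate". The other part, meant for a different kind of data, reads "a population pharmacokinetic model will be developed to analyse the sparse PK data". It does not say which women or samples belong to which dataset.

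The study-design paragraph of that section concerns "the exposure of various doses of sodium bicarbonate (i.e. 8.4g, 12.6g and 16.8g" (grams). Placebo is not mentioned, and sampling is described as following administration of sodium bicarbonate. No baseline correction, endogenous term or reference arm is stated. The population model is described as evaluating covariate effects on "physiological PK parameters (such as clearance and bioavailability", in a sentence that still refers to hydroxyurea.

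Elsewhere, Table 1 lists "Bicarbonate concentrations in plasma" at baseline, at every 30-minute point to 150 minutes and at birth, with no restriction by arm. The intervention paragraph describes a single intravenous bolus, and standard care for all women includes "intravenous fluid replacement (1.5 L of normal saline" per patient. The sample-size section says many women deliver within 30 minutes of baseline, and adds 192 women to 280 for that reason.

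**The concern.** Two problems meet here.

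First, non-compartmental analysis needs profiles dense enough to give an area and a terminal slope with little extrapolation. The only grid starts 30 minutes after dosing and stops at delivery, so the richest profiles come from the women who waited longest. That group is formed after randomisation.

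Second, bicarbonate is endogenous. The introduction says that accumulating lactic acid depletes maternal buffers, and every woman receives saline, so plasma bicarbonate can move without any drug effect. If the analysis has no reference for that movement, a fall in endogenous bicarbonate is attributed to elimination of the dose.

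Pharmacokinetics is a listed secondary outcome. The protocol measures bicarbonate to estimate the required dose and wants the results to inform dosing policy, so biased exposure or clearance estimates would carry into later decisions.

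**Working it through.** The plan gives no pharmacokinetic sample size or precision figure to reproduce. The checks below use its design figures and, where marked, assumptions.

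**1. Women without a second timed sample.** Sample-size section: 280 + 192 = 472. Implied share 192/472 = 40.7%.

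**2. How many profiles reach the later times.** Assume exponential times to delivery, set in two ways from the protocol's own figures.

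| Calibration | Undelivered at 90 min | Undelivered at 150 min |
|---|---|---|
| 40.7% delivered by 30 min | 21% | 7% (about 9 of 118 per arm) |
| Mean wait 110 min | 44% | 26% (about 30 of 118 per arm) |

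**3. Share of AUC inside the window.** Assume a bolus and mono-exponential decline with half-life h. The share of AUC(0–∞) between 30 and 150 minutes is 2^(−30/h) − 2^(−150/h).

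| h (min) | Before 30 | 30 to 150 | After 150 |
|---|---|---|---|
| 15 | 75% | 25% | 0.1% |
| 30 | 50% | 47% | 3% |
| 60 | 29% | 53% | 18% |
| 120 | 16% | 42% | 42% |
| 240 | 8% | 27% | 65% |

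Maximum over all h: put u = 2^(−30/h), so the share is u − u⁵. This is largest at u = (1/5)^(1/4) = 0.669, giving 0.535 at h ≈ 52 minutes. At least 46.5% is therefore extrapolated even with all five timed samples. If the last sample is at 110 minutes, the maximum is 44.7%.

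**4. Endogenous share of the measured value.** An 8.4% solution holds 8.4 g per 100 mL; at 84 g/mol this is 1 mmol/mL, so the doses are 100, 150 and 200 mmol. Assume 65 kg and a distribution volume of 0.3 to 0.5 L/kg, that is 19.5 to 32.5 L. Initial rise = dose/volume:
- 100 mmol: 3.1 to 5.1 mmol/L
- 200 mmol: 6.2 to 10.3 mmol/L

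Assume endogenous bicarbonate of 18 to 22 mmol/L (the upper value matches the exclusion above 22). The drug share runs from 3.1/(3.1 + 22) = 12% to 10.3/(10.3 + 18) = 36%, so 64% to 88% of the initial level is endogenous.

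**5. Spurious half-life from dilution alone.** Assume no true elimination, endogenous 20 mmol/L, and a fall caused by 1.5 L of saline taking effect over 120 minutes after baseline. With a fixed baseline subtracted, apparent half-life = 120 ln 2 / ln[rise/(rise − fall)]. The fall is 20 − 20 × 15/16.5 = 1.8 mmol/L if saline dilutes an assumed 15 L. If saline dilutes the drug's own volume, it is 20 × 1.5/34 = 0.88 (32.5 L) or 20 × 1.5/21 = 1.43 (19.5 L).

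| Drug volume | Fall (mmol/L) | 100 mmol | 200 mmol | Ratio |
|---|---|---|---|---|
| 32.5 L | 1.8 | 93 min | 238 min | 2.6 |
| 19.5 L | 1.8 | 190 min | 426 min | 2.2 |
| 32.5 L | 0.88 | 246 min | 537 min | 2.2 |
| 19.5 L | 1.43 | 255 min | 555 min | 2.2 |

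The absolute values depend heavily on the assumptions. The false dose-dependence, a little over twofold, appears in every row.

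**The case against.** Several stronger readings are tempting, and the documents do not support them.

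- *The placebo arm is left out.* A reader of the pharmacokinetics section alone might infer this. Its population paragraph excludes no arm, Table 1 schedules bicarbonate without restriction by arm, collectors are blinded and so cannot sample by arm, and the pharmacokinetic form in the data collection tool has a time-0 row. The values would exist; what is missing is a statement of their use.
- *The plan promises bioavailability.* It appears once, as a generic example of what population models evaluate, in text apparently carried over from hydroxyurea work. It is not a listed outcome. It is still not estimable here, because all dosing is intravenous.
- *Non-compartmental analysis is impossible.* A woman undelivered at 150 minutes has a baseline, five timed samples and a birth sample. That supports observed concentrations and a partial AUC, and a late birth sample can extend the window.
- *Placebo is the only way to identify drift.* With three randomised doses and linear kinetics, the intercept across doses also carries information on it. Placebo removes the need for that extrapolation and the linearity assumption, so it is the more robust source.
- *The false half-lives differ by four to five times.* That comes only from pairing 100 mmol at 32.5 L with 200 mmol at 19.5 L (93 against 426 minutes), which mixes dose with volume.

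Two further points stand. The protocol says bolus in one place and infusion in others, and gives no duration, so where the peak falls is unknown and the AUC bound holds for the bolus description. The timing of the saline relative to baseline is not given either. The plan does promise to adjust for relevant clinical information, and a competent modeller might add a baseline term, but nothing in the text requires one.

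**Conclusion.** The concern holds as a gap in the analysis plan, not in data collection. No intensive dataset is defined. On the bolus description, at most 53.5% of total AUC falls in the 30 to 150 minute window, and about 41% of women are implied to lack a second timed sample. Non-compartmental total AUC and clearance would be mostly or nearly half extrapolation, in a subgroup selected by waiting time.

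The absence of any endogenous reference is the more consequential part: drift can be read as elimination. The 64% to 88% endogenous share and the 2.2 to 2.6-fold spurious contrast are illustrations. They rest on assumed weight, volume, endogenous level and saline timing, and are not predictions. The AUC bound assumes mono-exponential decline. The issue affects a secondary outcome, not the primary pH analysis, and should be corrected because the remedy uses data already scheduled.

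**What to change.** Rewrite the pharmacokinetic data-analysis paragraph as follows.

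- Fit the population model to bicarbonate from all four arms, with each woman's time-0 value and an endogenous baseline and drift term informed by the placebo arm.
- Enter the dose as intravenous input with bioavailability fixed at 1, and include the birth sample at its actual time.
- Report the model-based rise over placebo at each dose.
- Drop the non-compartmental analysis. Alternatively, restrict it to a baseline-corrected partial AUC over the sampled window, in women meeting a stated minimum number of samples, labelled descriptive.
- Remove the bioavailability and hydroxyurea wording, and reconcile the pharmacokinetics section with Table 1 on samples, arms and method of bicarbonate measurement (chromatography in one, blood gas analyser in the other).
- Reconcile the bolus and infusion descriptions, and record actual start and stop times of administration so that the model's input is defined.

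Cost: revised text and somewhat more modelling work, since a drift term in truncated profiles is a real structural choice. There would be no model-free total AUC, which these samples could support only weakly. No extra blood samples are needed.

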3. BMI
4. Cardiovascular system
 - i. BP
 - ii. Pulse
 - iii. SPO2
5. Respiratory system
 - i. Respiratory rate
6. Abdominal examination
 - i. Does the participant have a visible Bandl's ring?
 - ii. Doe the participant have palpable uterine contractions?
 - iii. What is fetal heart rate?
7. Vaginal examination
 - i. Is the vulva and vagina oedematous?
 - ii. Is the caput present?
 - iii. Is the pelvis adequate?
 - iv. Have the membranes ruptured?
 - v. What is the colour of the liquor?

D. Baseline laboratory test results - Maternal

Parameter	Blood	Amniotic fluid	Urine
pH		Not Applicable	Not applicable
Blood gasses		Not Applicable	Not applicable
Lactate			

E. Study drug administration

Time	
Package number	

F. Maternal outcomes after study drug administration

Time (minutes)	Lactate in maternal blood sample	Lactate in amniotic fluid sample	Maternal arterial blood gasses	Maternal pH
0				
30				
60				
90				
120				
150				

G. Maternal outcomes at birth

1. Mode of delivery
 - i. SVD
 - ii. CS
2. For all those that delivered by CS, record the myometrial lactate here
3. What was the duration of labour?
4. Measured blood loss at birth
5. How well did the uterus contract after birth? (scale 1-10)
6. Assistant at delivery?
 - i. Midwife
 - ii. Specialist
 - iii. Medical Officer
 - iv. Intern
 - v. Student
 - vi. Others
7. Did the participant sustain any injuries in the birth canal?
 - i. Yes
 - ii. No

H. Newborn outcomes at birth

1. Record the Agar score here
 - i. At one minute
 - ii. At five minutes
2. Record the birth weight here
3. Lactate in arterial cord blood
4. Lactate in venous cord blood

Within one minute of child birth	Lactate in maternal blood sample	Lactate in amniotic fluid sample	Maternal arterial blood gasses	Maternal pH
Arterial cord blood				
Venous cord blood				

I. Monitoring of side effects and adverse events for 24 hours period after administration of study drug

(Tick all that apply)

1. Frequent urge to urinate		10. Swelling of feet or lower legs	
2. Headache (continuing)		11. Unpleasant taste	
3. Loss of appetite (continuing)		12. Increased thirst	
4. Mood or mental changes		13. Unusual tiredness or weakness	
5. Muscle pain or twitching		14. Venous irritation	
6. Nausea or vomiting		15. Cellulitis	
7. Stomach cramps		16. IV site pain	
8. Nervousness or restlessness			
9. Slow breathing			

J. Follow up outcomes

1. Perinatal outcomes on the 7th day postnatal
 - i. Alive and well
 - ii. Alive and not well
 - iii. Dead

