neonatal deaths despite being resuscitated. A potential way of improving maternal and perinatal outcomes among women with OL would be to buffer the excess lactic acid with sodium bicarbonate, achieving intrauterine resuscitation whilst awaiting an emergency cesarean section. However, in this situation, there is inadequate time (or staff) to correct the acidosis through careful titration of the bicarbonate infusion. A universal safe and effective dose would therefore facilitate its use. In our previous RCT, a single dose of 4.2g was insufficient to achieve changes in maternal or neonatal lactate levels. It is not known if a higher dose of bicarbonate would reverse the acidosis and achieve clinical benefits for the mother and baby. Therefore, we propose to undertake a placebo-controlled, dose-ranging pilot trial to determine the efficacy and safety of a preoperative infusion of sodium bicarbonate on acidosis, compared with placebo among women with obstructed labour (OL).

Justification

Undertaking a placebo-controlled, dose-ranging pilot trial shall establish a universal safe and effective dose of sodium bicarbonate for use to correct the acidosis among women with obstructed labour. Our results will inform the design of a full-scale effectiveness phase III trial to determine the effect of this preoperative infusion on maternal and perinatal outcomes. Furthermore, this information will facilitate the inclusion of sodium bicarbonate infusion in the standard preoperative preparation for women with obstructed labour in a low resource setting.

Objectives

General objective

To determine the efficacy and safety of a preoperative infusion of sodium bicarbonate on pH and lactate levels (metabolic acidosis) among women with obstructed labour.

Specific objectives

1. To determine the efficacy of a preoperative infusion of sodium bicarbonate on acidosis, compared with placebo among women with obstructed labour (OL).
2. To determine the safety of a preoperative infusion of sodium bicarbonate compared with placebo among women with obstructed labour (OL).

Hypothesis

We hypothesize that a higher dose of bicarbonate can safely lower the lactate levels (metabolic acidosis) by at least 20%.

Methods and materials

Study design

We will conduct a dose-finding phase III, randomized, double-blind, placebo-controlled, parallel-group trial.

Study setting

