Data analysis plan

Data will be analyzed using Stata version 17.0 (StataCorp; College Station, TX, USA). We will describe categorical variables as proportions and compare them with chi-squared tests or Fischer's exact tests as appropriate. We will describe continuous variables as means (SD) OR medians (IQR) and compare them with t tests or Mann-Whitney U tests as appropriate. Our analysis will be by intention to treat. To determine the safety of sodium bicarbonate infusion, we will compare the incidence of side effects in each arm and report risk differences.

For the primary outcome of acidosis (pH and lactate) between-subjects repeated measures ANOVA will be conducted. We will also conduct within-subject interaction repeated measures ANOVA to assess for differences in the rate of change of pH between the groups.

We will use histograms, P-P plots, k-density, and Q-Q to assess the distribution of normality of continuous outcomes. In case the distribution of normality is not met; we shall transform our data and this decision will be guided by Stata's *gladder* command that shows various transformation options.

All analyses will be followed by a Bonferroni posthoc test for multiple comparisons, a Friedman test to compare rates of change between the various groups, and a Mauchly's test of Sphericity to check for equal variance among the combinations of the various groups. We will use Margins and Margins plots to obtain marginal means and graphical descriptions of the interaction between various groups and time.

Data Monitoring

Independent Data Monitoring Committee (IDMC)

An independent data monitoring committee (IDMC) will be appointed consisting of 3 members: a statistician, an obstetrician/gynaecologist, and a paediatrician. They will operate according to the IDMC charter, which will be developed with the members. IDMC will be encouraged to follow the recommendations of the international DAMOCLES group for IDMC activities.[12] The IDMC will monitor the trial once with a focus on issues relating to the quality of trial conduct, such as overall and site-specific rates of recruitment, adherence to trial interventions, visit schedules, losses to follow-up, and administrative and safety data. It will review administrative and safety data approximately every three months. The treatment groups will be masked in the IDMC reports.

Interim analyses and stopping guidelines

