short turnaround time on blood results to inform clinical decision making. In the event of system downtime, we will use a YSTE-BG100 Blood Gas Analyzer (Yuesen Med, China) as a backup. The YSTE-BG100 is a compact and user-friendly device that can rapidly assess key parameters including pH, lactate, glucose, electrolytes, and blood gases [17], thereby ensuring continuity of care even when the RAPIDPoint® 500e Blood Gas System is down. In our previous trial the study drug was sourced from the local supplier accredited by the National Drug Authority (NDA). We intend to use 8.4% sodium bicarbonate (intervention), and sodium chloride 0.9% (placebo) from NEON laboratories Ltd, Mumbai, India.

Adverse events/side effects: Based on the package insert labelling for sodium bicarbonate and a review of the literature [18], we will actively monitor for the following; increased thirst, continuing loss of appetite, swelling of the lower limbs, venous irritation, muscle pain or twitching, continuing headache, nausea or vomiting, stomach cramps, unusual tiredness or weakness, nervousness or restlessness, mood or mental changes, frequent urge to urinate, slow breathing and cellulitis at the injection site. This will be done hourly for the first six hours, six hourly for the next 18 hours and then daily throughout the period of hospitalization.

Follow-on plan

We plan to publish our results in a peer reviewed journal irrespective of the findings, as we have demonstrated in the past. Furthermore, we have established contact with [name] in Oslo to advise on the setup of our current study. His group is undertaking similar work (<https://ichgcp.net/clinical-trials-registry/NCT05719467>), and they could be potential collaborators on a larger grant application if the results are positive (see attached support letter). We have a community advisory group that is crucial in disseminating our findings to the lay public. [name] is also a member of National Safe Motherhood Executive Committee (NASMEC), a ministry of health technical advisory group on maternal health. He will disseminate the findings in this group.

Table 2: Proposed study timelines

Activity	2024												2025					
	Jan	Feb	Mar	Apr	May	Jun	Jul	Aug	Sep	Oct	Nov	Dec	Jan	Feb	Mar	Apr	May	Jun
REC & UNCST approvals	*	*	*	*	*													
Recruitment of staff					*	*	*											
Procurements		*	*	*	*	*	*	*	*	*	*							
Data collection							*	*	*	*	*	*	*	*	*	*	*	*
Data analysis											*	*	*	*	*	*	*	*

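### The visible data form has no timed post-dose field for maternal vital signs or fetal heart rate, and the planned safety analysis leaves unused the serial blood gases and electrolytes that are collected: a cheap improvement

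*Combined protocol and SAP*

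**What the plan says.** Safety against placebo is the second specific objective. The Data analysis plan gives its only stated safety analysis: "we will compare the incidence of side effects in each arm and report risk differences".

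The Adverse events/side effects paragraph (under Management) lists the events to be actively monitored, ending with "frequent urge to urinate, slow breathing and cellulitis at the injection site". It then sets the timing: "This will be done hourly for the first six hours, six hourly for the next 18 hours", followed by daily checks while the woman is in hospital. The Data collection section adds that women will be examined and questioned about side effects.

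In Appendix 1, section C (clinical examination) has one entry each for blood pressure, pulse and SpO2, one for respiratory rate under "5. Respiratory system", and one for the fetus, "What is fetal heart rate". Section D holds baseline laboratory results and section E drug administration. The 24-hour record of harms, "I. Monitoring of side effects and adverse events for 24 hours period after administration of study drug", is a list of 16 symptoms to tick. It has no column for time, count, severity or onset.

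Table 1 schedules maternal blood gases, electrolytes and plasma bicarbonate at 0, 30, 60, 90, 120 and 150 minutes and at birth. Section F of the form has timed rows from 0 to 150 minutes for lactate, maternal gases and pH.

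**The concern.** The trial is meant to identify a dose that is safe as well as effective, and its safety conclusion will rest on symptom ticks. A tick list with no times cannot show when an event began, how long it lasted or how marked it was. Slow breathing is the clearest case: the form takes a respiratory rate in section C, yet afterwards the sign is reduced to yes or no with no stated threshold. A modest dose-related change in breathing, saturation or blood pressure after the sampling window could leave no trace in the data.

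The fetal side matters because the stated rationale is intrauterine resuscitation while the woman waits for caesarean section. The form shows no fetal observation between dosing and birth, so the fetal course over that interval cannot be compared by arm. The halting rule in the Independent Data Monitoring Committee section also depends on adverse-event occurrence in the active arms against placebo, so it draws on the same record.

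**Working it through.** **1. Where each measure can be recorded after dosing.** This covers the visible form (sections F to K) and Table 1.

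| Measure | Visible post-dose record |
|---|---|
| Blood pressure, pulse, SpO2, respiratory rate | None |
| Fetal heart rate | None |
| Maternal pH and gases | Section F, timed rows to 150 min; Table 1 also at birth |
| Sodium, potassium, calcium, chloride | Table 1 to 150 min and at birth; no column in section F |
| Bicarbonate | Table 1 as above; no column in section F. Section K has timed rows to 150 min that might hold it, but its heading names another drug |
| Symptoms, including slow breathing | Section I, one tick each for the whole 24 h |

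**2. Text against form.** Six hourly checks plus 18/6 = 3 six-hourly checks make 9 in the first 24 hours. Section I has one tick per symptom, so nine planned observations become one, without a time.

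**3. Coverage of the serial samples.** Sampling ends at 150 minutes (2.5 h) or delivery, against 24 h of safety monitoring. Sample size estimation and sampling says that many women deliver within 30 minutes of baseline with no second measurement, and adds 192 of the 472 participants (192/472 = 41%) for that reason. Table 1 does mark gases and electrolytes at birth, but the sample size section plans as if these women have only a baseline value.

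**4. Illustration of count against tick.** The plan gives no figure to reproduce. Only n = 118 per arm comes from the documents. Assumed: respiratory rate normal with SD 4 (range 3 to 5), mean 20 on placebo and 18 on an active arm, a tick placed below 12, two-sided 5%, one active arm against placebo.

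- *One counted rate, t-test.* Noncentrality = 2 / (4 × √(2/118)) = 3.84, giving power 97% (86% to 100% for SD 5 to 3).
- *Tick at a single look.* Probabilities are Φ((12 − 20)/4) = 2.3% and Φ((12 − 18)/4) = 6.7%. Exact Fisher power is 25% (4% to 29% for SD 3 to 5).
- *Tick if any of nine checks is below 12.* With within-woman correlation ρ, P(tick) = 1 − ∫ φ(z) [1 − Φ((12 − μ − 4√ρ z) / (4√(1 − ρ)))]⁹ dz. For ρ = 0.8 this is 7.6% against 18.5%, Fisher power 64%. For ρ = 0.5 it is 12.5% against 29.0%, power 86%.

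With 70 per arm, one counted rate has 84% and the one-look tick 10%.

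**5. What any yes/no item can show at 118 per arm.** The placebo incidence is assumed. 80% power needs a rise from 1% to about 8.9%, from 2% to about 11.0%, or from 5% to about 16.2%. Zero events in 118 leaves a two-sided 95% upper limit of 1 − 0.025^(1/118) = 3.1%.

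**The case against.** The strongest reply is Table 1. pCO2 is a direct, objective measure of hypoventilation and serum sodium of sodium load, and both are scheduled every 30 minutes in the period when a single bolus is most likely to act. A reader might infer that the safety objective lacks its most sensitive measures. The documents do not support that: early respiratory and metabolic effects are partly measured. What remains is that the Data analysis plan does not use these values for safety, that they end at 150 minutes or birth, and that they say nothing about blood pressure or fetal heart rate.

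A reader might also infer that the five signs are taken only before dosing. That rests on the order of the form. Section C has no time field, Figure 1 is not shown, and the text mentions examination, review of case notes and clinical data during the stay. The supportable statement is that no post-dose field is visible.

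Taking 25% as the power of the tick would be too harsh, because it assumes one look. With the nine scheduled checks, about 64% to 86% is the fairer comparison.

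A reader might add that staff who know the arm will bias the ticks. The Randomisation paragraph says data collectors stay blinded. The unequal infusion volumes raise a question about that, but it is a separate one and this point does not need it.

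Finally, fetal effect is not unmeasured: cord lactate, Apgar scores and day-7 status are collected. Only the interval from dosing to birth is uncovered.

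**Conclusion.** The point holds as a low-cost improvement to recording and analysis; it does not show that the safety objective is unassessed. Three things follow from the visible documents: no post-dose field for the five signs, nine scheduled checks reduced to one untimed tick list, and serial gases and electrolytes that no safety analysis names. The uncovered parts are the remainder of the 24 hours, blood pressure, and the fetus between dosing and birth.

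The size is illustrative: 97% power for one counted rate, against about 64% to 86% for a tick at any of nine checks. The mean, SD, fall, threshold and correlation are all assumptions. The comparison also supposes that the fall is present at the time analysed and that the midwife counts breaths and applies a fixed threshold each time. The threshold of 12 serves the calculation only and is not a proposed definition.

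**What to change.** **Form.** Add timed fields for blood pressure, pulse, SpO2, respiratory rate and, until birth, fetal heart rate, in section F at the 30-minute sampling visits and in section I at the scheduled side-effect checks. Make section I one dated and timed row per check, so that form and text agree, and record the counted rate beside the slow-breathing item. Add electrolyte and bicarbonate columns to section F.

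**Data analysis plan.** Add a sentence such as: *For each active arm against placebo, change from baseline in blood pressure, pulse, SpO2, respiratory rate and fetal heart rate (until birth), and in serial pCO2, pO2, sodium, potassium, calcium and bicarbonate, will be reported by time point with 95% confidence intervals and the number of women observed, next to the side-effect risk differences.* The number observed matters because sampling ends at delivery.

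**Cost.** No new staff or equipment is implied, since the signs are already on the baseline form and the visits are already planned. At most 5 sampling times plus 9 checks are affected in the first 24 hours, or 12 distinct times if the 60- and 120-minute samples coincide with hourly checks. The downside is more recording and data entry at those visits.
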